### 15.3 Database Quality Assurance

The clinical database will be reviewed and checked for omissions, apparent errors, and values requiring further clarification using computerized and manual procedures. Data queries requiring clarification will be generated and addressed by the investigational site. Only authorized personnel will make corrections to the clinical database, and all corrections will be documented in an audit trail.

### 16. Ethical aspects

#### 16.1 Ethics Committee

The protocol, ICF, and appropriate related documents must be reviewed and approved by an EC constituted and functioning in accordance with ICH E6, Section 3, and any local regulations. Any protocol amendment and/or revision to the ICF will be resubmitted to the EC for review and approval, except for changes involving only logistical or administrative aspects of the study (e.g., change in CRA[s] or change of telephone number[s]). Documentation of EC compliance with ICH and any local regulations regarding constitution and review conduct will be provided to the sponsor.

A signed letter of study approval from the EC Chairman must be sent to the Principal Investigator (if regionally required, the heads of the medical institutions) with a copy to the sponsor prior to study start and the release of any study drug to the site by the sponsor or its designee (ICH E6, Section 4.4). If the EC decides to suspend or terminate the study, the investigator (if regionally required, the heads of the medical institutions) will immediately send the notice of study suspension or termination by the EC to the sponsor. Study progress is to be reported to the EC annually (or as required) by the investigator or sponsor, depending on local regulatory obligations. If the investigator is required to report to the EC, he/she will forward a copy to the sponsor at the time of each periodic report. The investigator(s) or sponsor will submit, depending on local regulations, periodic reports and inform the EC (if regionally required, the heads of the medical institutions) of any reportable adverse events per ICH guidelines and local EC standards of practice. Upon completion of the study, the investigator will provide the EC with a brief report of the outcome of the study, if required.

### 16.2 Ethical Conduct of the Study

This study will be conducted in accordance with the standard operating practices of the sponsor (or designee), which are designed to ensure adherence to GCP guidelines as required by the following:

- Page 69 of 88 Date: April 04th, 2016
- In accordance to the principle of World Medical Association Declaration of Helsinki, 2013;
- ICH E6 Guideline for GCP (CPMP/ICH/135/95) of the European Agency for the Evaluation of Medicinal Products, Committee for Proprietary Medicinal Products, International Conference on Harmonization of Pharmaceuticals for Human Use;
- European Clinical Trial Directive 2005/28/EC, for studies conducted within any EU country.
   All SUSARs will be reported, as required, to the Competent Authorities of all involved EU member states:
- And other applicable regulatory authorities.

### 16.3 Subject information and Consent

As part of administering the informed consent document, the investigator must explain to each subject (or guardian/legally authorized representative) the nature of the study, its purpose, the procedures involved, the expected duration, the potential risks and benefits involved, and any potential discomfort. Each subject must be informed that participation in the study is voluntary and that he/she may withdraw from the study at any time and that withdrawal of consent will not affect his/her subsequent medical treatment or relationship with the treating physician. This informed consent should be given by means of a standard written statement, written in non-technical language. The subject should understand the statement before signing and dating it and will be given a copy of the signed document. If a subject is unable to read or if a legally acceptable representative is unable to read, an impartial witness should be present during the entire informed consent discussion. After the written informed consent form and any other written information to be provided to subjects is read and explained to the subject or the subject's legally acceptable representative, and after the subject or the subject's legally acceptable representative has orally consented to the subject's participation in the trial and, if capable of doing so, has signed and personally dated the ICF, the witness should sign and personally date the consent form. The subject will be asked to sign an informed consent at the Screening Visit prior to any study-specific procedures being performed. No subject can enter the study before his/her informed consent has been obtained. An unsigned copy of an EC and sponsor-approved written informed consent must be prepared in accordance with ICH E 6, Section 4, and all applicable local regulations and provided to the sponsor. Each subject must sign an approved informed consent prior to study participation. The form must be signed and dated by the appropriate parties. The original, signed ICF for each subject will be verified by the sponsor and kept on file, according to local procedure, at the study center.

The subject or the subject's legally authorized representative should be informed in a timely manner if new information becomes available that may be relevant to the subject's willingness to continue participation in the trial. The communication of this information should be documented.

### 17. Administrative procedures

## 17.1 Changes to the Protocol

There are to be no changes to the protocol without written approval from the sponsor. Protocols will be followed as written. Any change to the protocol requires a written protocol amendment or administrative change that must be approved by the sponsor before implementation. Amendments affecting the safety of subjects, the scope of the investigation, or the scientific quality of the study require submission to health or regulatory authorities as well as additional approval by the applicable EC of all investigational sites and, in some countries, by the regulatory authority. These requirements should in no way prevent any immediate action from being taken by the investigator, or by the sponsor, in the interest of preserving the safety of all subjects included in the study. If an immediate change to the protocol is felt by the investigator to be necessary for safety reasons, the sponsor's appropriate study team member must be notified promptly and the EC for the site must be informed immediately. A protocol change intended to eliminate an immediate hazard may be implemented immediately, provided that the Regulatory Authorities are subsequently notified by protocol amendment.

Changes affecting only administrative aspects of the study do not require formal protocol amendments or EC approval, but the EC (if regionally required, the heads of the medical institutions) must be kept informed of such changes. In these cases, the sponsor will send a letter to the EC (if regionally required, the heads of the medical institutions) detailing such changes.

#### 17.2 Adherence to the Protocol

The investigator will conduct the study in strict accordance with the protocol (refer to ICH E6, Section 4.5).

### 17.3 Monitoring Procedures

The sponsor's or CRO's CRA will maintain contact with the investigator and designated staff by telephone, and/or letter, and/or email between study visits. Monitoring visits to each investigational site will be conducted by the assigned CRA as described in the monitoring plan. The investigator (if regionally required, the heads of the medical institutions) will allow the CRA to inspect the clinical, laboratory, and pharmacy facilities to assure compliance with Good Clinical Practices and local regulatory requirements. The eCRFs and subject's corresponding original medical records (source documents) are to be fully available for review by the sponsor's representatives at regular intervals. These reviews verify adherence to the study protocol and data accuracy in accordance with federal regulations. All records at the investigational site are subject to inspection by the local regulatory agency.

In accordance with ICH E6, Section 6.10, source documents include but are not limited to the following:

Page 71 of 88 Date: April 04th, 2016

- Clinic, office, hospital charts;
- Copies or transcribed healthcare provider notes which have been certified for accuracy after production;
- Recorded data from automated instruments such as x-rays, and other imaging reports: e.g., sonograms, CT scans, MRIs, nuclear medicine scans, ECGs, rhythm strips, electroencephalograms (EEGs), polysomnographs, and pulmonary function tests (regardless of how these images are stored, including microfiche and photographic negatives);
- Records of telephone contacts;
- Drug distribution and accountability logs maintained in pharmacies or by research personnel;
- Laboratory results and other laboratory test outputs: e.g., urine pregnancy test result documentation;
- Correspondence regarding a study subject's treatment between physicians or memoranda sent to the EC;

### 17.4 Recording of Data

An eCRF is required and must be completed for each subject by qualified and authorized personnel. All data on the eCRF must reflect the corresponding source document. Any corrections to entries made on the CRF must be documented in a valid audit trail where the corrections must be dated, initialed, the reason for change stated, and original data not obscured. Only data required by the protocol for the purposes of the study should be collected.

#### 17.5 Retention of Records

The circumstances of completion or termination of the study notwithstanding, the investigator (if regionally required, the heads of the medical institutions) has the responsibility to retain all study documents, including but not limited to the protocol, the Investigator's Brochure, regulatory agency registration documents, ICFs, and EC correspondence. The investigational site should plan to retain study documents until at least 2 years after the last approval of a marketing application in an ICH region and until there are no pending or contemplated marketing applications in an ICH region or at least until 3 years have elapsed since the formal discontinuation of clinical development of the investigational product.

It is requested that at the completion of the required retention period or, should the investigator retire or relocate, the investigator contact the sponsor, allowing the sponsor the option of permanently retaining the study records.

### 17.6 Auditing Procedures and Inspection

In addition to routine monitoring procedures, the sponsor's Clinical Quality Assurance department conducts audits of clinical research activities in accordance with the sponsor's Standard Operating Procedures (SOPs) to evaluate compliance with the principles of ICH GCP and all applicable local regulations. A government regulatory authority may also wish to conduct an inspection (during the study or after its completion). If an inspection is requested by a regulatory authority, the investigator must inform the sponsor immediately that this request has been made.

## 17.7 Handling of Study Drug

All study drugs will be supplied to the Principal Investigator (or a designated pharmacist) by the sponsor. Drug supplies must be kept in an appropriate secure area (e.g., locked cabinet) and stored according to the conditions specified on the drug label. The investigator (a designated pharmacist) must maintain an accurate record of the shipment and dispensing of the study drug in a drug accountability ledger, a copy of which must be given to the sponsor at the end of the study. An accurate record of the date and amount of study drug dispensed to each subject must be available for inspection at any time. Once study drug has been received by the investigational site, the assigned CRA will review these documents along with all other study conduct documents at appropriate intervals during investigational site visits.

All drug supplies are to be used only for this protocol and not for any other purpose. The investigator (a designated pharmacist) must not destroy any drug labels or any partly used or unused drug supply prior to approval to do so by the sponsor. At the conclusion of the study and as appropriate during the course of the study, the investigator (a designated pharmacist) will either return all used and unused drug containers, drug labels, and a copy of the completed drug disposition form to the sponsor's designated contractor or, where approval is given by the sponsor, will destroy supplies and containers at the investigational site.

#### 17.8 Publication of Results

All manuscripts, abstracts, or other modes of presentation arising from the results of the study must be reviewed and approved in writing by the sponsor in advance of submission. The review is aimed at protecting the sponsor's proprietary information existing either at the date of the commencement of the study or generated during the study. The detailed obligations regarding the publication of any data, material results or other information, generated or created in relation to the study shall be set out in the agreement between each investigator and the CRO or the sponsor, as appropriate.

#### 17.9 Disclosure and Confidentiality

The contents of this protocol and any amendments and results obtained during the course of this study will be kept confidential by the investigator, the investigator's staff, and the EC and will not be disclosed in whole or in part to others or used for any purpose other than reviewing or performing the study without the written consent of the sponsor. No data collected as part of this study will be utilized in any written work, including publications, without the written consent of the sponsor. These obligations of confidentiality and non-use shall in no way diminish such obligations as set forth in the Confidentiality Agreement between the sponsor and the investigator.

All persons assisting in the performance of this study must be bound by the obligations of confidentiality and non-use set forth in the Confidentiality Agreement between the investigator and sponsor (provided by the sponsor).

## 17.10 Subject Insurance and Indemnity

The sponsor will provide the insurance in accordance with local guidelines and requirements as a minimum for the subjects participating in this study.

#### 18. Completion/Discontinuation of Subjects

## 18.1 Removal of Subjects from Therapy or Assessment

The sponsor reserves the right to discontinue the study for medical reasons or for any other reason at any time. If the study is prematurely terminated or suspended, the sponsor will promptly inform the investigators/institutions and the regulatory authority(ies) of the termination or suspension and the reason(s) for the termination or suspension. The IEC should also be informed promptly and provided with the reason(s) for the termination or suspension by the sponsor or by the investigator/institution, as specified by the applicable regulatory requirement(s).

The investigator may discontinue treating a subject with the study drug or withdraw the subject from the study at any time for safety or administrative reasons. The subject may decide to discontinue study drug or withdraw from the study at any time for any reason. The reason for discontinuation will be documented. If a subject discontinues study treatment, the subject will enter the follow-up period and be required to complete protocol-specified end of treatment visits, procedures, and survival follow-up unless the subject withdraws consent. The investigator should confirm whether a subject is withdrawing from study treatment but agreeing to continue protocol-specified, end of treatment study visits, procedures, and survival follow-up, or whether the subject is withdrawing consent. If a subject withdraws consent, the date will be documented in the source documents.

Subjects who have discontinued study treatment without progression should have disease assessments every 12 weeks from the date of the last assessment until disease progression is documented or another anti-cancer therapy is initiated.

EudraCT no.: 2015-001467-39

Page 74 of 88 Date: April 04th, 2016

All subjects will be followed for survival and all post disease progression cancer treatments administered will be recorded until death, except where a subject withdraws consent or the sponsor chooses to halt survival follow-up following completion of the primary study analysis.

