#### 7.3 Treatment phase

The treatment phase will begin at the time of allocation of the first subject and will consist of the study treatment cycles. The treatment phase will end when the last patient discontinues the study drug. Prior to the completion of the final primary study analysis, an individual subject will remain in the treatment phase until documentation of disease progression.

Subjects who discontinue study drug administration prior to disease progression will continue to be followed in the treatment phase according to the tumor assessment schedule listed in table 3 (performed at week 6 after the first dose of study drug and then, every 12 weeks or sooner if clinically indicated) until documentation of disease progression or start of another anticancer therapy.

Subjects will be allocated in each primary tumor cohort to receive lenvatinib 24 mg by continuous once daily oral administration. Subjects will undergo safety and efficacy assessment as defined in Table 3. Other reasons for discontinuation of study drug different from disease progression include development of unacceptable toxicity, withdrawal of consent or sponsor discontinuation of lenvatinib development.

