#### Tumor assessments

- Tumor assessments will be performed using RECIST 1.1. (Appendix I) Investigator determined response assessments will be performed at each assessment time point and entered onto the eCRF. Copies of all tumor imaging studies will be sent to an imaging core laboratory (Central Review) for prospective on-study primary efficacy assessment. Tumor assessments will be carried out following the guidelines provided by the study sponsor. Tumor assessments (CT of abdomen, and pelvis, and of all other known sites of disease) will be performed during the screening phase and, the first assessment will be performed 6 weeks after the first dose, the second assessment will be performed 12 weeks after the first dose, then every 12 weeks during study treatment cycles in the treatment phase or sooner if clinically indicated until documentation of disease progression.
- A brain CT/MRI will be performed at screening, as clinically indicated. In addition, for subjects with history of treated brain metastases, brain scans must be performed at screening and every tumor assessment time point.

- Page 38 of 88 Date: April 04th, 2016
- Data from somatostatin receptor schintigraphy or PET-CT (octreoscan) with specific radiolabeled agents for neuroendocrine tumors (such as Ga68, 5-HTP or F-Dopa) will be collected if available and performed within the 6 months prior to the first dose of study drug but are not acceptable as tumor assessment techniques during treatment phase.
- Data from bone scan will be collected, if available and performed within 6 months prior
  to first dose of study drug and every 24 weeks after first dose of study drug, and at the
  final visit unless the last scan was performed less than 24 weeks before.
- Somatostatin schintigraphy, PET and bone scan are not compulsory. They will be collected, if performed.
- A chest x-ray or skeletal x-ray that clearly demonstrates a new metastatic lesion may be used to document progression in lieu of the CT/MRI scans.
- Subjects who discontinue study drug prior to disease progression must continue to undergo tumor assessments every 12 weeks in the follow-up period, until disease progression is documented or another anti-cancer therapy is initiated.

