# 13. Trial development

## 13.1 Schedule of Visits and Procedures

Table 4 Schedule of Visits and Procedures

This table presents the schedule of visits and procedures for the screening, treatment and follow-up phases of this study.

Phase	Phase Screening Phase		Treatment Phase									
Period	Screening a,	Baseline a,	Study Treatment									Follow up
Visit	v1 -28 TO -2	V2 DAY -1	V3 C1D1	V4 C1 D7	V5 C1D15	v6 C2D1	v7 C2D15 W6	v8 C3D1	v9 C3D15	V10 C4D1 CXD1	EOT +28D LD	Every 6 months
Informed consent	Х											
Inclusion/exclusion	X	X										
Allocation		X										
Demographic data	X											
ECOG PS°	Х	X	Xa	X	Х	Х	X	Х	X	Х	Х	
pTNM staging	Х											
Med/Surg history	X	X										
Vitals signs d	X	X	Xa	Х	Х	Х	X	Х	X	Х	Х	
Physical exam f	X	Xe	Xa	Х	Х	Х	Х	Х	Х	Х	Х	
12-lead ECG g	Х					Х					Х	
Echocardiogram h	Х		Performed every 24 weeks following the first dose of study drug or sooner, if clinically indicated									
Biochemistry and hematology h	Х	X h	Xp	Х	Х	Х	X	Х	Х	Х	Х	
Urinalysis	Х	Х	Xb	Х	Х	Х	X	Х	Х	Х	Х	
Pregnancy test i	Х	Х	Xp									

EudraCT no.: 2015-001467-39

Mod.093; Version 02 dated 08/04/2009 SOP CT001

Phase	Screening Phase		Treatment Phase									FU Phase
Period	Screening a,	Baseline a,	Study Treatment							Follow up		
Visit	v1 -28 TO -2	V2 DAY -1	V3 C1D1	V4 C1 D7	V5 C1D15	v6 C2D1	v7 C2D15 W6	v8 C3D1	v9 C3D15	V10 C4D1 CXD1	EOT +28D LD	Every 6 months
Dispense Study Treatment			х			х		х		х		
Accountability Study Treatment			Х			x		х		x	х	
Tumor assessments (CT/MRI) j	Х		CT/MRI of abdomen/pelvis and other areas of known disease at screening plus any areas of newly suspected disease should be performed at week 6 after the first dose of treatment, 12 weeks after the first treatment dose and then, every 12 weeks or sooner if clinically indicated until documentation of disease progression									
Survival k				Х		х		х		х	Х	х
Biomarkers I		Х				х					Х	
Archival tumor blocks or slides m		x										
Concomitant medication	Х	Х	Х	Х	х	х	х	х	х	х	х	
AEs/SAEs p	х	х	Х	Х	х	х	х	х	х	х	х	

Page 43 of 88 Date: April 04th, 2016

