### 13.4 Record survival data. Post study treatment follow-up period procedures

After study drug discontinuation, subjects will be followed for survival during the Post Study Treatment Follow-Up Period. Survival data and other cancer treatments received will be collected every 6 months until close of the study database. The study sponsor may elect to discontinue survival follow-up at any time.

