#### 20.6 Sample Size and Accrual

Sample size has been calculated using single stage design. For considering Lenvatinib as an effective treatment, a success rate of ORR of at least 25% is expected. However, a success rate of 10% or less would be considered unacceptable. With 90% power and a 5% level of significance, a total of 55 patients for each cohort are required.

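### The protocol gives conflicting scan calendars for patients who stop lenvatinib before progression, so some can go from week 6 to week 18 without imaging; the expected effect on ORR is small

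*Protocol*

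**What the plan says.** **General calendar.** Protocol 12.2 (Tumor assessments) sets scans at weeks 6 and 12 after the first dose and every 12 weeks from there. Table 4 (13.1) agrees: after the week-6 scan, the next is "12 weeks after the first treatment dose and then, every 12 weeks or sooner if clinically indicated until documentation of disease progression". Section 7.4 also runs every 12 weeks starting at week 12.

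**Patients who stop before progression.**

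- 7.3 keeps them in the treatment phase, with scans "performed at week 6 after the first dose of study drug and then, every 12 weeks or sooner if clinically indicated". It attributes this schedule to table 3, which is the dose-reduction table.
- 7.3.1 says every 12 weeks with no starting point. Follow-up begins only at progression or new therapy.
- 12.2 says they "must continue to undergo tumor assessments every 12 weeks in the follow-up period", again with no starting point.
- 18.1 moves them to follow-up when they stop drug and says they "should have disease assessments every 12 weeks from the date of the last assessment until disease progression".
- 18.2 places them in follow-up on the regular assessment schedule.
- 13.4, on follow-up procedures, says "Survival data and other cancer treatments received will be collected every 6 months until close of the study database" and lists no imaging.

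**Use of the scans.** ORR is the proportion with a best overall response of CR or PR, by central review. It is analysed per cohort once the last patient has had the second assessment, at week 12 (20.5.1). Early tumor shrinkage (ETS) is defined at the week-6 scan (12.3), and the per-protocol definition names week 6 (20.2).

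**The concern.** Tumor measurements should be taken on the same clock whether or not the patient is still on drug. Here a site can follow one section faithfully and scan an early stopper on dates that another section contradicts. A response that would first show at week 12 may then be picked up six weeks later, or not at all if the data cut-off comes first. A patient who stops before week 6 may lack the scan on which ETS is measured. The phase label adds to the confusion: whether a stopper is still in the treatment phase decides which procedure list a site will consult, and the follow-up list in 13.4 mentions no scans.

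**Working it through.** **1. Scan weeks under each rule.** For 18.1, the next scan is the last scan plus 12 weeks. Screening scans may be up to 28 days before C1D1, so the last scan before a week-3 stop lies between week -4 and week 0.

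| Stop at | 12.2 / Table 4 / 7.4 | 7.3 read literally | 18.1 |
|---|---|---|---|
| Week 3 | 6, 12, 24 | 6, 18, 30 | first scan at -4 + 12 = 8 to 0 + 12 = 12 |
| Week 8 or 11 | 6, 12, 24 | 6, 18, 30 | 6, then 6 + 12 = 18, then 30 |
| Week 13 | 6, 12, 24 | 6 and 12 already done, then 18, 30 | 6, 12, then 12 + 12 = 24 |

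A stop between weeks 6 and 12 loses the week-12 scan under both 7.3 and 18.1. A stop at week 3 loses the week-6 scan under 18.1 only. A stop after week 12 loses neither.

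**2. The plan's own sample size.** Protocol 20.6 gives the inputs: "a success rate of 10% or less would be considered unacceptable", "a success rate of ORR of at least 25% is expected", and "With 90% power and a 5% level of significance, a total of 55 patients for each cohort are required". Neither the sidedness nor the decision rule is stated. With an exact one-sided binomial test, the smallest n reaching 90% power is 55, with success at 10 or more responses:

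- P(X ≥ 10 | n = 55, p = 0.10) = 0.0444
- P(X ≥ 10 | n = 55, p = 0.25) = 0.911

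So 55 is reproduced, and the scan conflict does not change it.

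**3. Who has no scan after week 6 at the cut-off.** The cut-off falls 12 weeks after the last patient starts. A week-18 scan precedes it if the patient enrolled at least 18 - 12 = 6 weeks before the last one. Recruitment is planned for about 18 months, or 78 weeks. With uniform accrual, the share enrolled too late is g = 6/78 = 0.077.

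**4. Effect on power.** The documents give no early-stopping rate, so these are assumptions:

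- d, the share of responders who stop in weeks 6 to 12: 5% to 20%
- f, the share of those whose response first shows at week 12: 25% to 100%

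The share of true responders not captured is q = d × f × g, and the observable rate is 0.25 × (1 - q).

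- Low end: q = 0.05 × 0.25 × 0.077 = 0.001; power 0.911
- High end: q = 0.20 × 1 × 0.077 = 0.0154; observable rate 0.246; power 0.900

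At the high end, the expected loss is 55 × 0.25 × 0.0154 = 0.21 responders per cohort, or 0.25 × 0.0154 = 0.4 points of ORR. One responder actually missed would move ORR by 1/55 = 1.8 points.

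**5. Sensitivity.** Setting g = 1, so that no later scan ever counts, gives q from 0.0125 to 0.20 and power from 0.90 down to 0.68. That case contradicts 7.3 and 18.1, which both provide a week-18 scan. It is shown only as an outer bound.

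**The case against.** The best reply is that the protocol has one calendar and one stray phrase. Sections 12.2, 7.4 and 18.2 and Table 4 all point to scans tied to the first dose. The bracket in 7.3 may be shorthand for the assessment table it meant to cite. Its week-6 scan also covers the week-3 stopper, who loses it only if 18.1 is read alone. This limits the size of the problem but does not remove it. The rule in 18.1 is explicit and written for exactly these patients, and the reference in 7.3 leads to the wrong table.

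Three stronger readings are tempting, and the documents do not support them.

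- **That early stoppers lose the scan on which ORR is measured.** ORR is best overall response. Week 12 only sets the cut-off through the last patient, so a week-18 scan counts for anyone enrolled early enough.
- **That imaging ends at drug stop.** Section 13.4 is silent on scans but does not end them, and 7.3, 7.3.1, 12.2, 18.1 and 18.2 all require them. The tumor-assessment entry in Table 4 is one running text, and the available text does not show whether it covers the follow-up column.
- **That PFS is biased by a quantifiable amount.** SAP Table A (4.2) censors treatment discontinuation for toxicity or other reasons at the last radiological assessment, and protocol 20.7 also treats discontinuation as censored. On the natural reading, these patients are censored around drug stop whichever scan calendar applies.

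**Conclusion.** The protocol is internally inconsistent on when, and in which phase, patients who stop before progression are scanned. The exposed patients are those who stop before week 12. Stops in weeks 6 to 12 can lose the week-12 scan under 18.1 or literal 7.3, and stops before week 6 can lose the week-6 scan under 18.1. The expected cost to the primary analysis is small: power of 0.900 to 0.911, against 0.911 with no loss. That range assumes uniform accrual over 78 weeks, the stated ranges for d and f, and that a response present at week 12 can still be seen at week 18. The sample size stands, and no PFS bias is claimed. The point is worth correcting because the affected scans feed ORR and ETS, and because the correction is cheap.

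**What to change.** Refer 7.3, 7.3.1, the bullet on stoppers in 12.2, 13.4 and 18.1 to one imaging calendar: the existing Table 4 calendar, anchored to the first dose and applied whatever the treatment status, until progression or the start of another anticancer therapy. In particular:

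- remove the restart of the clock at the last assessment in 18.1;
- replace the bracket in 7.3 with a reference to Table 4, and correct the reference to table 3;
- state in 13.4 and Table 4 that patients without progression continue imaging after stopping drug;
- use one phase label for these patients throughout.

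The cost is protocol wording. For the few early stoppers, scans fall earlier than under 18.1, including the later ones in the series, and some patients have one additional scan. No new type of procedure is needed, and the sample size stays at 55 per cohort.
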